Three hundred and sixty veterans diagnosed with TRMD will be enrolled at 9 VA Medical Centers over a three year period. Participants will be randomized into a double blind clinical trial to left prefrontal rTMS treatment or to sham (control) rTMS treatment (180 participants each group) for up to 30 treatment sessions. All participants will be evaluated on a wide variety of measures including cognitive, neurological and functional parameters. All will meet DSM-IV criteria for Major Depression and all will have failed at least two prior pharmacological interventions as defined by the Antidepressant Treatment History Form (ATHF) (Sackeim et al. 1990), i.e., they are TRMD patients. Veterans with PTSD or history of substance abuse will not be excluded but detailed history regarding these disorders will be obtained. Participants will also not be required to stop using anti-depressant medication. The primary dependent measure will be remission rate ($HRSD24 \leq 10$), and secondary analyses will be conducted on other indices. Comparisons between the rTMS and the sham groups will be made at the end of the acute treatment phase to test the primary hypothesis.

Protocol

I. INTRODUCTION AND BACKGROUND

A. Importance of Treating Treatment-Resistant Major Depression (TRMD)

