1. Target: In order to meet the target of randomizing 360 participants within three years, the Study Chairman will select 9 potential VA sites for participation based on the availability of a large number of TRMD patients with relevant co-morbidities and the willingness and ability of the site to carry out the protocol. Each site will be expected to randomize at least 40 eligible patients over the three year recruitment period of the study. The VA sites that have expressed an interest in participating in this study and who treat a substantial number of relevant TRMD patients within a 3 year period can be found in Appendix N.

2. Methods: The Site Investigator (SI) and the Study Coordinator (SC) (hired at each site to work full-time on this project) will be responsible for patient recruitment. They will work closely with the site clinical staff to insure that the purpose and scope of the study, including eligibility criteria, are fully explained at the beginning of the study. Site staff will be told who to contact to refer a potential study participant. Study participants will be selected from the entire cohort of patients referred for outpatient or inpatient psychiatric treatment at the participating sites. In consultation with the SI, the patient's referring physician will continue to manage the general psychiatric care of each of the participants. The primary care physician and SI will work together with respect to management of the subject's care while participating in the study.

3. Patient Pool: The SIs and the SCs should expect to screen in person as many as 2-3 potential patients for every eligible consenting participant and will enroll (consent) 720-800 patients with concomitant disease at the local sites. The Human Studies Subcommittee and/or IRB will review any posters or advertisements used before being posted. It is essential to maintain a flow of patients for screening throughout the three year recruitment period.

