To randomize a patient into the study, the SI or the SC will submit the electronic randomization form. This computerized system, after verifying eligibility, will randomize a patient to either the rTMS or to the sham rTMS treatment group. A non-sequential treatment number will be assigned. This unique treatment number will be key entered into the device which will be associated with a treatment assignment and will enable the rTMS device to deliver the appropriate treatment (active or sham) to each patient. Every attempt will be made to randomize a participant so that he/she will receive his/her first rTMS treatment as soon as possible after randomization. Non-sequential treatment numbers will be assigned to ensure that investigators cannot initiate a participant on treatment before randomization. An adaptive randomization scheme will be used so that approximately equal numbers of patients will be randomized to each treatment group within several important subsets. These subsets include patients with a substance abuse disorder and patients with PTSD. Enrolling site will also be

incorporated into the adaptive randomization scheme. A “biased coin” procedure will be used to make an assignment that will improve overall balance more likely than an assignment that will not (Efron 1971). Imbalance will be calculated by summing the marginal totals for these three factors for each treatment group and calculating the difference, D. If the imbalance is less than three, assignments will be made with equal probability; otherwise, the probability of assigning to the group that will increase imbalance will be $1/D$. This approach will be incorporated within the electronic data capture system.

D. Duration of the Study

The duration of the study will be three and a half years, with a three year enrollment period. Each participant will be in the trial for a total of approximately 29-39 weeks (2-4 weeks screening, 4-11 weeks acute treatment phase and 24 week follow-up phase).

E. Intervention Procedure

The overview of the experimental design and procedures is presented in Figure 2.

[figure not shown]

Figure 2: Overview of Research Design

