All data collected for this study will be handled and used in compliance with both the CSP and the Perry Point CSPCC data security plans. All patient level data will be treated as protected health information. Data will be transmitted from participating sites using secure servers. Study personnel at CSPCC, CRPCC, and at participating sites will be required to complete annual training courses. These courses will cover good clinical practices, human subjects' protection, cyber security, and privacy policy. Any data security breaches will be immediately reported. Access to patient level data at CSPCC or CRPCC, will be obtained through user accounts which will be protected by strong passwords. File protections will be used to limit access to members of the study group. Patient level data will never be stored on portable storage devices unless it is encrypted, explicitly authorized, and use specific.

VIII. BIOSTATISTICAL CONSIDERATIONS

A. Sample Size

The primary hypothesis of the study is that in VA patients with TRMD, rTMS will result in a greater remission rate at the end of acute treatment than sham rTMS. The primary outcome measure in this study is success or failure to achieve remission from depression as defined by a score on the Hamilton Rating Scale for Depression (HRSD24) of 10 or less. The primary analysis will be done as an “intent-to-treat” analysis, i.e. patients will be analyzed in the groups to which they were randomized and drop-outs will be considered treatment failures. The primary hypothesis will be addressed using a logistic regression model with PTSD diagnosis, history of substance abuse, and site as covariates.

Based on review of the studies reported in the Introduction Section, the Planning Committee felt that a 10% difference between treatments would be of clinical relevance given the severity of the illness. With a sample size of 180 per group, the proposed study will have a power of 81% to detect an absolute difference between groups of 10% in the percentage of those participants who remit (6% sham and 16% rTMS). Thus, a total of 360 patients will be randomized. This goal of 360 patients, larger than any previous study, also provides a measure of protection should some assumptions be wrong.

B. Analysis Plan

1. Site Effects and Baseline Comparability

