Site effects will be tested using a logistic regression analysis examining the effect for Treatment in a model that includes Site and Site x Treatment interaction. Baseline comparability among the treatment groups will be evaluated with respect to such variables as demographics (e.g., age, gender, race), baseline values of outcome measures (e.g., the HRSD, QOL measure(s), suicidality, etc.), antidepressant currently being used, etc. Chi-square and analysis of variance techniques, as appropriate, will be used to determine any differences in distribution of the variables across the treatment groups. Any variable that appears to be different between the groups ($p < 0.10$) will be evaluated to determine whether such imbalances had any effect on conclusions.

2. Analysis of Primary Outcome Measure

The primary outcome measure in this study is success or failure to achieve remission from depression after a maximum of 30 sessions of rTMS or sham treatment. “Remission” is defined by a score on the HRSD24 of 10 or less after a maximum of 30 sessions of treatment. The primary analysis will be done as an “intent-to-treat” analysis, i.e. patients will be analyzed in the groups to which they were randomized, and patients who dropout before completing the Acute Treatment Phase will be considered treatment failures for the primary analysis on remission rates. The primary analyses and several secondary analyses will be conducted on outcome measures such as “remission” and “response” which are binary and defined by specific criteria. Logistic regression models with PTSD diagnosis, history of substance abuse, and site as covariates will be used for these analyses.

C. Additional Analyses

In addition to the main analysis using the entire randomized or “intent-to-treat” cohort, logistic regression models will be used for “completers” and also for “fully compliant” subjects to provide further information about treatment effects. For example, it would be expected that if rTMS had a significant clinical effect, its effect would appear greater in “completer” and “totally compliant” cohorts, than in the entire randomized cohort. Other analyses will be performed on secondary measures to further provide useful clinical information.

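### At the planning rates, the logistic Site x Treatment model will almost always meet site-by-arm cells with no remission, so the check of consistency across sites is unreliable as specified; the primary analysis is not affected

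*Protocol*

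**What the plan says.** Section VIII.B.1 (Site Effects and Baseline Comparability) tests site effects by a "logistic regression analysis examining the effect for Treatment in a model that includes Site and Site x Treatment interaction". It gives no test statistic, no significance level for the interaction, and no provision for cells without events. The sentence does not name its outcome; the binary endpoint around which the section is built is remission.

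The design values come from elsewhere in the protocol:

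- Executive Summary, Design and Methods: "Three hundred and sixty veterans diagnosed with TRMD will be enrolled at 9 VA Medical Centers", with "180 participants each group".
- Section VI.A.1: "Each site will be expected to randomize at least 40 eligible patients over the three year recruitment period of the study".
- Section VI.C: enrolling site is "incorporated into the adaptive randomization scheme", so the arms should be close to equal within site.
- Section VIII.A: "With a sample size of 180 per group, the proposed study will have a power of 81" percent, for remission rates of "6% sham and 16% rTMS". Drop-outs count as failures, so all 360 patients stay in the denominator.

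The primary model is a different one. Sections VIII.A and VIII.B.2 specify logistic regression with PTSD diagnosis, history of substance abuse and site as covariates, and no interaction.

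**The concern.** A model with Treatment, Site and their interaction fits each site-by-arm cell freely. Its fitted probability in a cell is the observed proportion there. If a cell has no remission, its fitted log-odds runs to minus infinity and the interaction coefficient for that site has no finite estimate. With remission planned to be rare and cells of about 20, this would be the usual case.

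At stake is the plan's check that the treatment effect is consistent across sites. Depending on the statistic that the software prints, the check could suggest heterogeneity that is not there or could fail to show heterogeneity that is. Choosing a repair after seeing which sites had no remissions would be a data-driven choice.

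**Working it through.** **Inputs.** 360 patients, 9 sites, 180 per arm (Executive Summary; VI.A.1). This gives 360 / 9 = 40 per site and, with balance within site (VI.C), 20 per cell in 18 cells. Remission rates are 6% and 16% (VIII.A). Two assumptions: exactly 20 per cell in the base case, and a nominal 5% level for the interaction test, since the protocol states none.

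**The plan's own figure.** Two-sided 5% test of two proportions with continuity correction:

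- mean rate 0.11; null SE = √(2 × 0.11 × 0.89 / 180) = 0.03298
- alternative SE = √((0.06 × 0.94 + 0.16 × 0.84) / 180) = 0.03256
- power = Φ((0.10 − 1/180 − 1.96 × 0.03298) / 0.03256) = Φ(0.915) = 82.0%

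The stated 81% is close to this. Fisher's exact test gives 83.3%, and the uncorrected test 86.1%. The planning figures are therefore a fair basis for what follows.

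**Empty cells.**

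- Expected remissions per cell: 20 × 0.06 = 1.2 on sham; 20 × 0.16 = 3.2 on active.
- P(sham cell empty) = 0.94^20 = 0.290. P(active cell empty) = 0.84^20 = 0.031.
- P(a given site has remissions in both arms) = (1 − 0.290) × (1 − 0.031) = 0.688.
- P(at least one empty cell) = 1 − 0.688^9 = 0.965.
- Expected number of empty cells = 9 × (0.290 + 0.031) = 2.9 of 18.
- P(the reference site is affected) = 1 − 0.688 = 0.31. In that case the Treatment coefficient under reference coding is infinite or undetermined. If effects are averaged over sites, any empty cell suffices, so the figure is 96.5%.

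With unequal sites (20 to 60 patients) the chance of an empty cell is 98.3%. With equal sites whose remission rates vary (SD 0.5 on the logit scale) it is 97.4%.

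**Size of the interaction test.** 20,000 simulated trials for each pair of rates, equal cells, no interaction on the logit scale, each statistic compared with chi-square on 8 df at nominal 5% (simulation SE at most about 0.2 points):

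| Sham / active | Any empty cell | Likelihood ratio | Wald | Score |
|---|---|---|---|---|
| 6% / 16% (plan) | 96.5% | 8.6% | 0.0% | 4.0% |
| 6% / 6% | 99.8% | 9.0% | 0.0% | 1.4% |
| 3% / 20% | 99.9% | 3.7% | 0.0% | 5.6% |
| 10% / 20% | 71.9% | 10.1% | 0.03% | 4.7% |
| 20% / 30% | 10.6% | 7.8% | 1.6% | 5.3% |

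The empty-cell column is exact binomial. Repeat simulations at the planning rates put the likelihood-ratio rate between 8.6% and 9.2%. The 3% / 20% row uses the remission rates that section I.B reports from a single-site NIH study.

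The Wald result has a simple cause. A site with an empty cell has an effectively infinite standard error and adds nothing to the statistic, while the reference distribution keeps 8 df.

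**The case against.** A reader might infer more than the documents support, in four ways.

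- *That the primary result is undermined.* It is not. The primary model has site as a main effect only. A site is lost to it only when neither arm has a remission, and such a site carries no information on treatment anyway. The chance that this happens at some site is 1 − (1 − 0.290 × 0.031)^9, about 7.7%. Nothing in the protocol makes the primary analysis depend on the interaction test.
- *That the check cannot be computed.* It can. The likelihood stays bounded, so the likelihood-ratio statistic is finite, and the score statistic needs only the main-effects fit.
- *That every estimate fails.* Sites with remissions in both arms keep finite odds ratios.
- *That false positives are the harm.* That holds for likelihood ratio at the planning rates, but not at 3% / 20%, and Wald errs the other way.

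Three further objections carry some weight. The choice of statistic and the handling of sparse cells often belong in a SAP, which is not at hand. But the protocol itself fixes this model, and the model misbehaves at the protocol's own planning values, so the point is not an omission. Section VIII.C also examines site in the random regression of HRSD, which has no empty-cell problem; that is useful, but it concerns a different outcome and does not repair the check on remission. Finally, if remission were much more common than planned, or the check were applied to a more frequent outcome such as response, empty cells would be less common.

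**Conclusion.** The point holds for the supporting check of consistency across sites, and only there. At the planning values a fully finite maximum-likelihood fit of the Site x Treatment model is available in only about 3.5% of trials (100 − 96.5). At a conventional 5% level, the same data and model give a test that practically never rejects (Wald), one that rejects nearly twice too often (likelihood ratio, about 9%), or one close to nominal (score, about 4%). The plan does not say which.

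This rests on about 20 patients per cell and on rates near 6% and 16%. It is robust to unequal sites and to moderate variation between sites. It weakens clearly only at rates well above plan: at 20% / 30% the chance of an empty cell is 10.6%. The change is worth making before unblinding, because it is cheap and removes a choice that would otherwise follow the data.

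**What to change.** In section VIII.B.1:

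1. State that the treatment effect is taken from the main-effects primary model and is not read from the interaction model.
2. Replace the standard maximum-likelihood interaction test with one prespecified sparse-data method, for example Zelen's exact test of homogeneous odds ratios or a Firth-penalised likelihood-ratio test, and state its level.
3. Report remission rates by arm and risk differences for each site descriptively.

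The cost is wording and slightly more analysis work. Sample size, data collection and the primary test do not change. Power to detect site heterogeneity will be low whichever method is chosen, so a non-significant result should not be reported as evidence that sites agree.

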Our hypotheses will be tested in a three and a half year randomized double blind clinical trial of rTMS in TRMD. Three hundred and sixty participants will be recruited from 9 VA sites where they have been evaluated on a wide variety of measures including cognitive, neurological and functional parameters. All will meet DSM-IV criteria for Major Depression and all will have at least two failed pharmacological interventions as defined by the ATHF (Sackeim et al. 1990), i.e. they are TRMD patients. The primary dependent measure will be remission rate (HRSD24 \leq 10) at the end of the acute treatment phase, and secondary analyses will be conducted on other indices.

V. PATIENT POPULATION

The inclusion/exclusion criteria are designed to identify patients with TRMD who exhibit a full range of the manifestations of that condition. Furthermore, the population is intended to be representative of the VA's pool of patients with TRMD.

A. Inclusion Criteria

1. Between 18 and 80 years of age.
2. Using the Structured Clinical Interview for DSM Disorders (SCID) for DSM-IV-TR (First et al. 2002) patients will be diagnosed MDD.
3. Have a HRSD24 \geq 20 no more than 7 days prior to randomization.
4. Exhibit moderate level of resistance to antidepressant treatment defined, using the ATHF (Sackeim et al. 1990), as failure of at least two adequate medication trials.
5. Duration of current episode of MDD \leq 10 years.
6. Ability to obtain a Motor Threshold (MT) (should be determined at the end of the screening process).
7. Currently under the care of a VA psychiatrist.

8. If on a psychotropic medication regimen, that regimen will be stable for at least 4 weeks prior to randomization to the study and patient will be willing to remain on a stable regimen during the acute treatment phase.
9. Has an adequately stable condition and environment to enable attendance at scheduled clinic visits.
10. For female participants, agrees to use one of the following acceptable methods of birth control
 - Complete abstinence (not having sexual intercourse with anyone)
 - An oral contraceptive (birth control pills)
 - Norplant
 - Depo-Provera
 - A condom with spermicide
 - A cervical cap with spermicide
 - A diaphragm with spermicide
 - An Intrauterine device
 - Surgical sterilization (having your tubes tied)
11. Able to read, verbalize understanding and voluntarily sign the Informed Consent Form prior to performance of any study-specific procedures or assessments.

B. Exclusion Criteria

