In these exploratory analyses, alternative measures might prove to have different abilities to predict response to rTMS. Our consultant, [name] is an expert in the use of signal-detection methods to make such determinations (Kraemer, 1992). Because of the potential that collinearity may be a problem among potential moderators and mediators, [name] proposes that any examination of effects of the proposed predictor variables be corrected for the potential effect of initial level of severity of depression.

D. Assessing Size of Treatment Effect

Although data analyses can indicate the statistical significance of results, a statistically significant result does not in and of itself imply that a finding is useful in a practical sense. Therefore, in addition to testing for statistical significance, we will convey practical significance by reporting treatment effect sizes and their confidence intervals (Kraemer & Kupfer, 2006). We believe that such evaluations will yield conclusions that are directly relevant to the development of treatment programs of the type proposed here.

E. Supplemental Statistical Analyses

We will examine the degree of convergent validity between depression measures that are gathered on the same days. The analyses proposed are not presented as a complete list of all analyses likely to be performed. They simply provide a brief outline of the major statistics that will be obtained.

F. Economic Analysis

We will collect and report information on the incremental health care cost of rTMS based on its implementation at multiple VA medical centers (see **Appendix M**). Specifically, we will estimate the incremental per patient program (or direct) cost of rTMS relative to usual care over the course of an rTMS treatment (lasting no more than 11 weeks for most study participants) in our proposed implementation). Sensitivity analyses will be used to derive upper and lower estimates of resource use and incremental costs.

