In order for the DMC to make its recommendation for continuation of the study, it will be necessary for them to see the analyses for the primary outcome measure every time that the report is run and it is possible to calculate the primary outcome measure. Periodic monitoring of interim results can significantly affect the probability of making an incorrect decision. A number of formal techniques have been developed for interpreting interim results. At the organizational meeting, the DSMB will select the technique that it wants to use to monitor the study. Suggested techniques are the Haybittle-Peto and Lan-DeMets group sequential boundaries. For the Haybittle-Peto method, a constant z-statistic is used as the monitoring boundary. The Lan-DeMets procedure produces decision boundaries that are quite conservative over the first several looks and then gradually converges to the nominal alpha levels as the final look is approached. **Figure 3** gives an example of the Lan-DeMets boundaries for five looks at an alpha level of 0.05

Figure 3. Lan De - Mets Group Sequential Monitoring Boundaries

The patient characteristics by site that are given to the Investigators will also be considered by treatment group by the DMC. Differences between treatment groups on these patient characteristics may indicate a need to use any significantly different characteristics as covariates for the outcome measures. Formal testing of the differences between treatment groups will be done at the study's conclusion. Analyses of variance techniques will be used to test characteristics that are continuous in nature, while chi-square techniques will be used for the discrete variables.

As with any clinical trial, the safety of the patient will be of utmost concern. Safety will be monitored closely during the course of the study and the adverse event data will be reported in the primary study manuscript. Data will be collected on adverse events throughout the study. The DSMB Report will include data on incidence of adverse events by treatment group. It will also include data on early terminations and treatment dropouts.

Analysis of the primary outcome is discussed in the Statistical Section of the protocol. In addition to the primary outcome, the protocol lists a number of other outcome measures that will be considered. These include:

1. Depression measured by Montgomery-Asberg Depression Rating Scale, (MADRS)
2. Suicide Ideation measured by Beck Scale for Suicide Ideation (BSS)

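### Baseline HRSD24 is left out of the prespecified primary logistic model; adding it would give a small gain in precision and protect against chance imbalance in severity

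*Protocol*

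**What the plan says.** Sections VIII.A and VIII.B.2 of the protocol fix the same primary model. The first addresses the primary hypothesis "using a logistic regression model with PTSD diagnosis, history of substance abuse, and site as covariates". The second says "Logistic regression models with PTSD diagnosis, history of substance abuse, and site as covariates will be used for these analyses", referring to binary outcomes such as remission and response.

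These covariates match the adaptive randomisation in Section VI.C. On the balanced subsets it says "These subsets include patients with a substance abuse disorder and patients with PTSD", and it adds enrolling site as the third factor.

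Baseline HRSD24 is available. Inclusion criterion 3 (Section V.A) requires a score of at least 20, taken "no more than 7 days prior to randomization". A footnote to Table 2 repeats the timing, and item 5 of the randomisation form (Appendix E, Form 02) records the score.

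Baseline differences are handled in two further places:
- Section VIII.B.1 plans tests of baseline comparability and names the HRSD among the variables. It then takes "Any variable that appears to be different between the groups" at p<0.10 and examines whether the imbalance affected the conclusions.
- Appendix D, Section V, says that differences between arms "may indicate a need to use any significantly different characteristics as covariates for the outcome measures", with formal testing at the end of the study and no threshold given.

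For the moderator analyses, Section VIII.C.b proposes that predictor effects "be corrected for the potential effect of initial level of severity of depression".

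**The concern.** Remission is an absolute cut, HRSD24 of 10 or less, and entry runs from 20 upwards with no ceiling. A patient entering at 20 must fall 10 points to remit; one entering at 35 must fall 25. Starting severity is thus a natural candidate predictor of the primary outcome, and the protocol lists it as a possible moderator. It is neither a randomisation factor nor a covariate.

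Two things are at stake. First, a prognostic covariate left out of a logistic model costs some power, to a degree that depends on how prognostic it is. Second, if one arm happens to start more severe, that imbalance stays in the primary estimate. The p<0.10 check in Section VIII.B.1 is no remedy. In a randomised trial a baseline test detects only chance, its p-value says nothing about prognostic strength, and an imbalance that matters can pass unflagged. Appendix D adds looseness, because it leaves open that covariates might be chosen after data by arm have been seen.

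**Working it through.** **Inputs from the protocol.** 180 per arm, remission 6% sham and 16% rTMS, power 81% (Section VIII.A); nine sites (Section IV); PTSD 39% and substance abuse 45% among veterans with depression (Section I.I). The power statement gives no alpha, so two-sided 0.05 is assumed.

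**The plan's own figure.** For two proportions, power = Φ[(d − c − 1.96·SE0)/SE1], where d = 0.10, SE0 = √(2·0.11·0.89/180), SE1 = √((0.06·0.94 + 0.16·0.84)/180), and c = 1/180 is the continuity correction. This gives 82.0% with the correction and 86.1% without. The stated 81% is reproduced closely by the corrected form. The simulations below use a likelihood ratio test, so they start nearer 87–88%.

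**Average effect of adding baseline HRSD24.** The protocol gives no baseline-to-remission relation, so a range is assumed: odds ratio (OR) of remission per SD of higher baseline score. The planned model was simulated with 2,000 trials per row, a normal baseline score, and no effect of PTSD, substance abuse or site on remission. The Monte Carlo standard error is about 0.7 points.

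| OR per SD | Without baseline | With baseline |
|---|---|---|
| 1.0 | 87.4% | 87.4% |
| 0.8 | 88.2% | 87.8% |
| 0.67 | 88.4% | 88.4% |
| 0.5 | 87.1% | 88.4% |
| 0.4 | 87.3% | 89.0% |

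Type I error at OR 0.5, with 6% remission in both arms: 6.0% without and 5.9% with (standard error about 0.5). The two do not differ.

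A second set (1,500 trials each) truncates the baseline at 20, with an assumed SD of 4.1 and an assumed baseline-to-end correlation r. Power goes from 89.7% to 89.8% (r = 0.2), 87.9% to 89.5% (0.3), 88.7% to 90.2% (0.4), 88.2% to 90.1% (0.5) and 88.0% to 91.1% (0.6). A third set (2,000 trials each), with an untruncated baseline and 12% dropout counted as failure, gives gains of 0.2, 0.2, 1.2, 2.7 and 4.8 points at the same correlations. The 12% is assumed, from the 88% retention quoted for an earlier trial in Section I.E.

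**Effect of an unflagged imbalance.** Let the active arm start 0.17 SD more severe. Then z = 0.17/√(2/180) = 1.61 and p is about 0.11, so a 0.10 rule does not flag it. Simulated power (1,500 trials each, without the PTSD, substance abuse and site terms):

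| OR per SD | Without baseline | With baseline |
|---|---|---|
| 0.67 | 83% | 88% |
| 0.5 | 80% | 88% |
| 0.4 | 78% | 91% |

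At OR 0.5 the median treatment odds ratio without adjustment falls from 3.05 when balanced to 2.69. An imbalance the other way inflates it. An imbalance this large against the active arm occurs in about 5% of trials (half of 0.11), and the average gains above already include such trials.

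**Model size.** Expected remissions: 180·0.06 + 180·0.16 = 10.8 + 28.8 = 39.6. The planned model has 1 (treatment) + 1 (PTSD) + 1 (substance abuse) + 8 (sites) = 11 terms besides the intercept. Baseline score makes 12, so events per term go from 39.6/11 = 3.6 to 39.6/12 = 3.3.

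**The case against.** A reader might infer that the plan finds its primary covariates by testing baseline variables at p<0.10. The text does not support that. The covariates are named in advance, twice and identically, and match the randomisation factors. Section VIII.B.1 presents the p<0.10 step as a check on conclusions. Appendix D is looser, but it says only that differences may point to a need for covariates, within a description of what the monitoring committee reviews. That wording is worth closing off; it is not a selection rule.

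A reader might also see the severity correction in Section VIII.C.b as inconsistent with the primary model. The reason given there is collinearity among candidate moderators in exploratory work, which does not carry over to the randomised comparison.

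Other points on this side have weight. Adjusting for the randomisation factors alone is a defensible choice. Severity is not ignored: it is among the variables checked for balance, and the random regression analysis of HRSD uses baseline data. Response is a percentage fall from baseline, so the argument from the absolute cut does not apply to it directly. The strength of the baseline relation is assumed throughout, and the gain vanishes if it is weak. The model is already rich for about 40 remissions. An analysis plan not at hand may add adjusted analyses.

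These points limit the size of the matter. They do not defeat adding one prespecified covariate to a model that already spends eight terms on site, and the protocol itself fixes the covariate list.

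**Conclusion.** The point stands as a recommended improvement in precision and robustness. The primary model omits a baseline value already collected on the scale that defines the outcome. The planned test remains valid: there is no bias on average and no effect on type I error.

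The average power gain is about 0 to 3 points over most of the assumed range. It is essentially nil for a weak relation, and reached 4.8 points only at a correlation of 0.6 in one set of simulations. In the uncommon case of an adverse but unflagged severity imbalance of 0.17 SD, adjustment recovers roughly 5 to 12 points (the rounded figures differ by 5, 8 and 13). All of this rests on assumed baseline-outcome relations and, in one set, an assumed baseline SD of 4.1.

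It would go too far to say that power is lost whatever the relation. Any figure for how often baseline tests flag something by chance is also conditional. For the seven variables that Section VIII.B.1 gives as examples it would be 1 − 0.9^7 = 52% if they were independent, and correlation among the clinical scales would probably lower it.

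**What to change.** Before unblinding:
- Add baseline HRSD24, as a continuous covariate, to PTSD, substance abuse and site in the primary remission model, with the same wording in Sections VIII.A and VIII.B.2. As a secondary matter, do the same for response.
- State in Section VIII.B.1 and in Appendix D, Section V, that baseline significance tests will not change the primary model. Summarise baseline characteristics by arm descriptively.

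The cost is one degree of freedom, taking events per term from about 3.6 to 3.3. No new data are needed, since the score is already on the randomisation form. The treatment odds ratio would then be conditional on severity as well, so the absolute difference in remission, which is the basis of the sample size, should be reported beside it.
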